This study will assess the benefit to both the patient and health care system by allowing patients to safely undergo outpatient or short-stay Total Knee Arthroplasty (TKA) with improved postoperative pain and function with a short-duration tourniquet treatment protocol which includes the FDA-approved Aquamantys Bipolar sealer (Medtronic, Minneapolis, MN). The Aquamantys Bipolar Sealer is a single use, sterile, bipolar device intended to be used in conjunction with the Aquamantys Pump Generator for delivery of radiofrequency (RF) energy and saline for hemostatic sealing and coagulation of soft tissue and bone at the operative site. It is intended for, but not limited to orthopaedic, spine, thoracic and open abdominal surgery.

This study will provide invaluable information for both surgeons and hospital administrators to use when comparing potential treatment options for knee arthroplasty patients, with the end goal of making clinically meaningful improvements to patient care. It will also highlight the clinical importance of maintaining early quadriceps function. Quadriceps dysfunction has been linked to the amount of postoperative swelling (Holm et al., Arch Phys Med Rehabil, 2010). Anecdotally, we have seen a dramatic reduction in the amount of swelling present at the patient's first physical therapy visit on the day of surgery when utilizing a short-duration tourniquet protocol including the Aquamantys. By using Aquamantys to minimize effusion as part of a tourniquet-less TKA protocol, patients may be able to avoid loss of quadriceps function, which may then provide both short- and long-term benefit. Tourniquet-less TKA may reduce complications and readmissions by theoretically reducing fall risk by maintaining quadriceps function. Improved quadriceps function not only reduces fall risk but may allow patients to more rapidly achieve functional milestones after surgery such as walking without an assistive device and navigating stairs.

Objectives

List your research objectives. Please include a summary of intended research objectives in the box below.

The specific goals of study are to compare quadriceps strength, pain, opioid consumption, and patient function during the first three months in the setting of short-stay TKA between patients treated with short-duration tourniquet TKA with the Aquamantys® bipolar sealer versus those treated with the standard of care (tourniquet used throughout the case and no Aquamantys®).

Study Design

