Describe and explain the study design (e.g., observational, secondary analysis, single/double blind, parallel, crossover, deception, etc.).

- *Clinical Research:* Indicate whether subjects will be randomized and whether subjects will receive any placebo.
- *Community-Based Participatory Research:* If you are conducting [community-based participatory research \(CBPR\)](#), describe strategies for involvement of community members in the design and implementation of the study, and dissemination of results from the study.
- *Qualitative research:* Indicate ranges where flexibility is needed, if a fixed interview transcript is not available, describe interview topics including the most sensitive potential questions.
- *Research Repositories:* If the purpose of this submission is to establish a Research Repository (bank, registry) and the material you plan to collect is already available from a commercial supplier, clinical lab, or established IRB approved research repository, provide scientific justification for establishing an additional repository collecting duplicate material. Describe the repository design and operating procedures. For relevant information to include, see the [UK Research Biospecimen Bank Guidance](#) or the [UK Research Registry Guidance](#).

This is a single site, randomized, double-blind study which will be conducted at the University of Kentucky. This study intends to enroll 70 male and female participants. Participants will be randomized to have TKA either with the aforementioned short-duration tourniquet TKA protocol with Aquamantys or the standard of care (tourniquet used throughout the case with no Aquamantys). Provided patient meet the functional goals necessary for discharge, all patients will be discharged to home on the day of surgery or on postoperative day 1. Participants will be blinded during the course of the study to their assigned group, as will the study personnel performing postoperative assessments and the study's biostatistician.

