In order to determine an appropriate sample size, an a priori power analysis was performed. We chose to use isometric quadriceps strength at two weeks as the primary outcome variable. Using an alpha level of 0.05 and the standard deviation and minimal clinically important difference reported by Husted et al. (Trials, 2018) of 0.22 Nm/kg and 0.15 Nm/kg, respectively, a sample size of 70 total patients (35 patients per group) would be 80% powered to detect clinically important differences (G*Power, version 3.1).

Data collection will coincide with four regularly-scheduled patient visits: preoperative and 2, 6, and 12 weeks after surgery. Participants will complete isometric quadriceps testing at each study visit, and will be asked to complete the KOOS,JR, VR-12, and VAS pain scale questionnaires. We will also record the participant's opioid consumption per our standard of care, as well as whether the patient is able to walk without an assistive device and/or self-reports the ability to navigate stairs. Beginning at the 6-week postoperative visit, patients will be asked to complete the five times sit-to-stand test. The primary outcome variable, isometric quadriceps strength at 2 weeks, will be compared between groups using a two-tailed independent t-test. All continuous secondary variables will be assessed using group x time repeated measures ANOVAs. The prevalence of patients that can walk without an assistive device and/or navigate stairs at 2, 6, and 12 weeks will be compared between groups using chi-square or Fisher Exact tests as appropriate.

Attachments

Subject Recruitment Methods & Advertising

Describe how the study team will identify and recruit subjects. Please consider the following items and provide additional information as needed so that the IRB can follow each step of the recruitment process.

- How will the study team identify potential participants?
- Who will first contact the potential subjects, and how?
- Will you use advertisements? If so, how will you distribute those?
- How and where will the research team meet with potential participants?
- If applicable, describe proposed outreach programs for recruiting women, minorities, or disparate populations.
- How you will minimize undue influence in recruitment?
- Attach copies of all recruiting and advertising materials (emails, verbal scripts, flyers, posts, messages, etc.).

For additional information on recruiting and advertising:

- [IRB Application Instructions - Advertisements](#)

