On the contrary, recent research has identified the practice of short-duration tourniquet only when cementing in the TKA implants to be a safe alternative to long-duration tourniquet use (Wang, 2018). In a recent meta-analysis by Wang et al., short duration tourniquet use was associated with improved early functional outcomes but also with increased intraoperative blood loss when compared to long-duration tourniquet use. However, the prevalence of blood transfusions did not differ between short- and long-duration tourniquet use.

In the current study, participants randomized to the short-duration tourniquet group will only have the tourniquet inflated when cementing the components (approximately 5-10 minutes). The second difference is that the Aquamantys Bipolar Sealer will be used as part of the short-duration tourniquet protocol. The Aquamantys Bipolar Sealer will be used to seal open vessels in the posterior joint capsule to lessen intraoperative bleeding to ensure adequate cement fixation and potentially reduce intraoperative blood loss and postoperative effusion.

Isometric Quadriceps Strength Testing: The participant will sit in a seated position and a stabilizing strap will be placed around the bottom of the participant's shank and attached to a hand-held dynamometer. The participant will be asked to slowly kick the foot as hard as they can into the dynamometer pad placed on the anterior aspect of the participant's distal tibia. One practice trial followed by 3 actual trials will be performed. The participant will receive a 30-second rest in between each trial and a 1-minute rest in between legs for each test to prevent fatigue.

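### Should the plan add a bleeding outcome and a by-arm adverse-event table, given that it cites more blood loss with a short tourniquet?

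*Combined protocol and SAP*

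**What the plan says.** Research Procedures explains that a tourniquet inflated throughout the operation has traditionally served to limit blood loss. It then cites a meta-analysis linking short-duration use to "improved early functional outcomes but also with increased intraoperative blood loss when compared to long-duration tourniquet use". The next sentence reports that "the prevalence of blood transfusions did not differ between short- and long-duration tourniquet use", and the practice is introduced as a safe alternative. The sealer's role in the experimental arm is "to lessen intraoperative bleeding to ensure adequate cement fixation and potentially reduce intraoperative blood loss and postoperative effusion".

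The background text above Objectives speaks of "allowing patients to safely undergo outpatient or short-stay Total Knee Arthroplasty (TKA) with improved postoperative pain and function" and adds that "Tourniquet-less TKA may reduce complications and readmissions by theoretically reducing fall risk by maintaining quadriceps function". Objectives is narrower. It sets out to compare "quadriceps strength, pain, opioid consumption, and patient function during the first three months in the setting of short-stay TKA".

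Study Design states: "Data collection will coincide with four regularly-scheduled patient visits: preoperative and 2, 6, and 12 weeks after surgery". The outcomes it names are quadriceps strength, KOOS JR, VR-12, VAS pain, opioid consumption, walking without a device, stairs and the sit-to-stand test. It names no blood loss, transfusion, complication or readmission outcome. Participants are blinded, "as will the study personnel performing postoperative assessments" and the biostatistician.

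Records, Privacy, and Confidentiality commits to monitoring and recording every adverse event. Data and Safety Monitoring assigns real-time monitoring to investigators and coordinators. Neither section describes a tabulation by arm.

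**The concern.** Bleeding appears three times in the trial's reasoning: as the reason for the control practice, as the cited drawback of the short tourniquet, and as the reason for adding the sealer. A reader would expect to see it among the outcomes. The named collection times are clinic visits, with nothing listed for the operation or the hospital stay. Blood loss that led to no complication might also never be logged as an adverse event. The background mentions safety, complications and readmissions, and no comparison of these is planned.

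The stake is interpretive. If strength improves in the experimental arm, readers will ask at what cost in bleeding or harm. Without a stated table, the answer would be an unplanned look at the record, in a trial of a device supported by its manufacturer.

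**Working it through.** **The plan's own figure.** Study Design gives SD 0.22 Nm/kg, difference 0.15 Nm/kg, alpha 0.05 with a two-tailed t-test, and 80% power. The standardised difference is 0.15/0.22 = 0.682. The noncentral-t calculation gives 34.75 per arm, rounded up to 35, so 70 in total. Power at 35 per arm is 80.3%. The stated size reproduces, and no bleeding quantity enters it.

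**Objectives against outcomes.**

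| Stated objective | Measured by |
|---|---|
| Quadriceps strength | Isometric testing at all four visits; primary at 2 weeks |
| Pain | VAS |
| Opioid consumption | Recorded under standard care |
| Function | KOOS JR, VR-12, walking, stairs, sit-to-stand from 6 weeks |

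Every objective has a measure. Bleeding, complications and readmissions belong to the rationale, where the claims are hedged, and not to the objectives.

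**What added data could show at 35 per arm.** The documents give no blood-loss SD and no event rates, so the mean difference is in SD units and the event counts in the last item are assumed.

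- Mean blood loss, 95% CI half-width = t(0.975, 68) × √(2/35) = 1.995 × 0.2390 = 0.477 SD.
- Difference detectable with 80% power (two-sided t-test, alpha 0.05): 0.68 SD.
- Half-width no larger than 0.25 SD: 124 per arm gives 0.2501 and 125 gives 0.2491, so 125 per arm are needed, against 35 planned.
- Zero events in one arm: exact two-sided 95% upper bound = 1 − 0.025^(1/35) = 10.0%.
- Illustrative 3/35 against 1/35: 8.6% − 2.9% = 5.7 points, Newcombe 95% CI −7.2 to +19.7, Fisher p = 0.61.

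These would be descriptive estimates only. They could not show whether the sealer offsets the extra loss cited for a short tourniquet.

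**What is already collected.** All adverse events are to be recorded, and each participant has a randomised arm. A by-arm table needs nothing further.

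**The case for a change.** The strongest case for acting is that recording events is not the same as planning an analysis, and that naming the table in advance removes discretion over what is shown. The reassuring transfusion evidence is described in terms of tourniquet duration and does not mention the sealer, so it does not answer the question for the combined protocol. The added work would be modest: record abstraction for about 70 patients, with no new procedure and no change in sample size.

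Much of this stands. The text plans no bleeding outcome and no by-arm summary, and one sentence on the latter would be good practice. Three things limit its force.

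- It would be too strong to say that the trial plans no safety data, because all adverse events are to be recorded and monitored.
- Adding blood loss relies on facts the documents do not establish: that it is routinely recorded, and that someone other than the blinded assessors could abstract it. The values would also come from an unblinded surgical team.
- Absence from the forms cannot be shown. The flow chart, device form, memo and visit case report forms were not available. The four attachments under Data Collection & Research Materials are not a full data list, since strength, sit-to-stand and opioid use are collected without a matching form there.

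The application also treats bleeding as background and not as an open question. It describes the device as used for an approved indication and as part of the investigator's standard of care, and says both tourniquet methods are in current use. Leaving bleeding out of a 70-patient strength trial is a defensible choice of scope.

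**Conclusion.** No change to the plan follows. The omission is real on the text, but it contradicts no stated objective, rule or number. The primary comparison, its power and the secondary comparisons are untouched. The by-arm adverse-event table is a reporting detail that an analyst would supply from data already planned. The bleeding outcome is a reasonable preference with limited yield: about ±0.48 SD on mean blood loss, and an upper bound of 10.0% after no events in 35 patients.

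This rests on adverse events being recorded for all participants as promised, and on 35 per arm being analysed. It also rests on the report making no claim that the combined protocol is equivalent or superior on bleeding, complications or readmissions, which the trial could not support.

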- This modification may or will increase risk to study participants.

Is this modification request due to an Unanticipated Problem/Adverse Event, or Protocol Violation?

- Yes
- No

In your professional opinion, does this modification involve information that might relate to a subject's willingness to continue to take part in the research?

- Yes
- No

If yes, state how the information will be communicated to subjects (i.e., re-consent, send letter, etc.):

For each proposed modification, include a justification.

Example: [name], is being added as co-investigator because she has expertise with the subjects on this protocol. She has completed human subject protections training, and is authorized to obtain consent.

We are removing [name] as he is no longer at UK and adding [name] as he will take over data collection/analysis on the project.

PROJECT INFORMATION**0 unresolved
comment(s)**

Title of Project: (Use the exact title listed in the grant/contract application, if applicable).

If your research investigates any aspect of COVID-19, please include "COVID19" at the beginning of your Project Title and Short Title

Comparison to short-duration tourniquet Total Knee Arthroplasty (TKA) with the Aquamantys® bipolar sealer and the standard of care in the setting of outpatient TKA: A randomized, double-blinded study

Short Title Description

Please use a few key words to easily identify your study - this text will be displayed in the Dashboard listing for your study.

Aquamantys

Anticipated Ending Date of Research Project: 5/31/2024

Maximum number of human subjects (or records/specimens to be reviewed) 73

After approval, will the study be open to enrollment of new subjects or new data/specimen collection? Yes No

PI CONTACT INFORMATION

0 unresolved
comment(s)

Principal Investigator (PI) role for E-IRB access

The PI is the individual holding primary responsibility on the research project with the following permissions on the E-IRB application:

1. Read;
2. write/edit;
3. receive communications; and
4. submit to the IRB (IR, CR, MR, Other Review*).

If research is being submitted to or supported by an extramural funding agency such as NIH, a private foundation or a pharmaceutical/manufacturing company, the PI listed on the grant application or the drug protocol must be listed as PI here.

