**"Minimal risk" means that the probability and magnitude of harm or discomfort anticipated in the research are not greater in and of themselves from those ordinarily encountered in daily life or during the performance of routine physical or psychological examination or tests.

*****For Expedited and Exempt Applications, the research activities must be Risk Level 1 (no more than minimal risk to human subjects).*****

Refer to [UK's guidance document](#) on assessing the research risk for additional information.

SUBJECT DEMOGRAPHICS

0 unresolved comment(s)

Age level of human subjects: (i.e., 6 mths.; 2yrs., etc.) to **Study Population:**

Describe the characteristics of the subject population, including age range, gender, ethnic background and health status. Identify the criteria for inclusion and exclusion.

Provide the following information:

- A description of the subject selection criteria and rationale for selection in terms of the scientific objectives and proposed study design;
- A compelling rationale for proposed exclusion of any sex/gender or racial/ethnic group;
- Justification for the inclusion of vulnerable groups such as children, prisoners, adults with impaired consent capacity, or others who may be vulnerable to coercion or undue influence.

Please consider these resources:

[NIH Diversity Policy](#)

[FDA Diversity Guidance](#) 

Inclusion:

- 18 - 85 years of age
- Elected to have standard of care total knee arthroplasty
- Able to provided informed consent
- English speaking
- Able to participate in required follow-up visits and to complete study procedures and questionnaires

Exclusion:

- Participants undergoing revision arthroplasty
- Undergoing simultaneous bilateral arthroplasty
- Unicompartmental arthroplasty
- Functional, cognitive, or social limitations that do not allow safe discharge to home on either postoperative day 0 or 1

Attachments

Indicate the targeted/planned enrollment of the following members of minority groups and their subpopulations. Possible demographic sources: [Census Regional Analyst Edition](#), [Kentucky Race/Ethnic Table](#), [Kentucky Population Data](#).

(Please note: The IRB will expect this information to be reported at Continuation Review time for Pre-2019 FDA-regulated Expedited review and Full review applications):

Participant Demographics				
	Cisgender Man 	Cisgender Woman 	TGNB/TGE 	Unknown/Not Reported

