- For each source or method described, please list or attach all data to be collected (such as genetic information, interview scripts, survey tools, data collection forms for existing data, etc.).
- If you will conduct a record or chart review, list the beginning and end dates of the records you will view.

Please view the attached documents

Attachments

Attach Type	File Name
DataCollection	Knee Function Questionnaire.docx
DataCollection	KOOS-JR-2015.pdf
DataCollection	Visual Analogue Scale.docx
DataCollection	VR12.pdf

Resources

Describe the availability of the resources and adequacy of the facilities that you will use to perform the research. Such resources may include:

- Staffing and personnel, in terms of availability, number, expertise, and experience;
- Computer or other technological resources, mobile or otherwise, required or created during the conduct of the research;
- Psychological, social, or medical services, including equipment needed to protect subjects, medical monitoring, ancillary care, or counseling or social support services that may be required because of research participation;
- Resources for communication with subjects, such as language translation/interpretation services.

All research procedures will be carried out at the UK Good Samaritan Hospital and UK Healthcare Joint Reconstruction and Replacement offices. The participants will be followed by [name] and his research team which includes physicians, physician assistants, and clinical research coordinators during the study.

Potential Risks & Benefits

Risks

- Describe any potential risks – including physical, psychological, social, legal, ability to re-identify subjects, or other risks. Assess the seriousness and likelihood of each risk.
- Which risks may affect a subject's willingness to participate in the study?
- Describe likely adverse effects of drugs, biologics, devices or procedures participants may encounter while in the study.
- *Qualitative research* - describe ethical issues that could arise while conducting research in the field and strategies you may use to handle those situations.
- Describe any steps to mitigate these risks.

Benefits

- Describe potential direct benefits to study participants – including diagnostic or therapeutic, physical, psychological or emotional, learning benefits. This cannot include incentives or payments.
- State if there are no direct benefits.
- Describe potential benefits to society and/or general knowledge to be gained.

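### Does the missing conversion from dynamometer reading to Nm/kg leave the primary outcome undefined?

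*Combined protocol and SAP*

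**What the plan says.** The Study Design section names isometric quadriceps strength at 2 weeks as the primary outcome, compared between groups by a two-sided independent t-test. It takes the standard deviation and the minimal clinically important difference from a published trial, "of 0.22 Nm/kg and 0.15 Nm/kg, respectively", and arrives at 35 participants per group for 80% power. The sentences that define the outcome and the test carry no unit.

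The Research Procedures section describes the test: a seated participant, a strap at the lower shank and a hand-held dynamometer. The instruction is: "The participant will be asked to slowly kick the foot as hard as they can into the dynamometer pad placed on the anterior aspect" (distal tibia). Then: "One practice trial followed by 3 actual trials will be performed". Rest is allowed between trials and between legs, so both legs appear to be tested. The text does not mention the knee-to-pad distance, body mass, torque or a trial summary.

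Under Data Collection & Research Materials the form asks applicants to "please list or attach all data to be collected". The answer is "Please view the attached documents", followed by four files: a knee function questionnaire, KOOS JR, a visual analogue scale and VR-12. The Research Procedures section attaches a study flow chart, and the section on records and confidentiality refers to electronic case report forms for each visit. The content of the flow chart and of those forms is not available.

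**The concern.** A hand-held dynamometer normally reports a force. To get Nm/kg, that force must be multiplied by the distance from the knee to the pad and divided by body mass. The procedure mentions neither quantity, and no listed file is, by its name, a strength or body-measurement form. A reader could conclude that the analysed variable will not be the one on which the trial was sized.

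The missing items differ in kind. The formula, the leg and the trial summary can be fixed on paper at any time before unblinding. The lever arm has to be measured on the participant. If it was never recorded, that participant has no value in Nm/kg, or the whole analysis moves to a scale for which the plan gives no standard deviation and no clinically important difference. An unstated trial summary also leaves some freedom of choice at the analysis stage.

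**Working it through.** **1. The plan's own figure.** Inputs from Study Design: difference 0.15, standard deviation 0.22 (both Nm/kg), two-sided alpha 0.05, 1:1 allocation, independent t-test.

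- Standardised difference: d = 0.15 / 0.22 = 0.682.
- Noncentrality at 35 per group: d × √(35 × 35 / 70) = 0.682 × 4.183 = 2.852, on 68 degrees of freedom, critical value 1.995.
- Power from the noncentral t distribution: 80.3%.
- Solving for 80% power: n = 34.75, rounded up to 35 per group, 70 in total.

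The stated size reproduces. It makes sense only on the Nm/kg scale, so the intended scale is clear although the outcome sentence omits the unit.

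**2. Do the file lists show that the inputs are missing?** Compare what the plan says it collects with the files it names.

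| Item | Stated as measured or recorded | Form identifiable by file name |
|---|---|---|
| Isometric strength | Study Design; Research Procedures | none |
| Five times sit-to-stand | Study Design; Research Procedures | none |
| Opioid consumption | Study Design | none |
| Adverse events | Records, Privacy, and Confidentiality | none |
| KOOS JR, VR-12, visual analogue scale, knee function questionnaire | Study Design; Research Procedures | one each |

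The attachments cover the questionnaires and nothing else. Strength itself is certainly measured and has no listed form. A missing file name therefore says almost nothing about whether lever arm or body mass is recorded. The place to look is the electronic case report forms, which are not shown. Body mass could also come from the medical record.

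**3. Which leg?** The exclusion criteria include "Undergoing simultaneous bilateral arthroplasty", so each participant has one operated knee at the index surgery. The operated leg is the only sensible reading.

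**4. Maximum or mean of three trials.** Let w be the within-session standard deviation of a single trial; the documents give none, so w = 0.10 Nm/kg is assumed. For three independent normal errors, the error variance is w²/3 = 0.333w² for the mean and about 0.559w² for the maximum. The gap is 0.226 × 0.01 = 0.00226. The planned variance is 0.22² = 0.0484.

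- If 0.22 belongs to the mean and the maximum is analysed: variance 0.0484 + 0.00226 = 0.05066, standard deviation 0.225, d = 0.666, power 78.5%.
- If 0.22 belongs to the maximum and the mean is analysed: variance 0.0484 − 0.00226 = 0.04614, standard deviation 0.215, d = 0.698, power 82.1%.

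Either way the change from 80.3% is under 2 percentage points. A smaller w gives a smaller change.

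**5. What lost values would cost.** With the same d, power is 79.7% at 35/34, 76.6% at 32/32 and 70.7% at 28/28. These are figures for missing data from any cause; nothing in the documents shows that such losses arise here. Project Information allows up to 73 participants. At 37/36 power is 81.9%, and three could be lost with 70 remaining, although Study Design states an intended enrolment of 70.

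**The case for a change.** The strongest counter-argument is timing. A lever arm that was not measured by the 12-week visit cannot be obtained at any scheduled visit after that, and the application gives "Anticipated Ending Date of Research Project: 5/31/2024". A form check costs almost nothing, while the loss, if it has occurred, would be permanent and the sample size has little to spare. It is also true that, on the visible text alone, the primary value cannot be computed.

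The last point stands as a description of the text. The timing argument depends on an omission that the documents do not show. A team that chose Nm/kg for its power calculation presumably meant to compute it; that is an inference, not proof, but no evidence points the other way. Even if the lever arm were missing throughout, force per kilogram could still be compared between randomised groups. The link to the stated standard deviation and difference would be lost, but the comparison would remain valid.

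On freedom of choice, participants are blinded, "as will the study personnel performing postoperative assessments", and so is the biostatistician. That limits picking a trial summary by its result. It does not replace naming one, but step 4 shows how little the choice is worth.

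**Conclusion.** No change to the plan follows. The observation is accurate: the visible procedure does not say how a reading becomes Nm/kg or which summary of the three trials is primary. This is missing detail in an ethics application form, of a kind that analysts fill sensibly before unblinding: operated-leg torque per kilogram of body mass at 2 weeks, with one trial summary named in advance. Confirming that the case report forms hold lever arm and body mass is ordinary housekeeping.

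If those inputs are recorded, there is no effect on sample size, on the stated power (80.3% at 35 per group) or on the validity of the comparison. The trial-summary choice is worth less than 2 points of power, given a within-session standard deviation of no more than 0.10 Nm/kg and the same treatment difference on either summary. The conclusion would change only if the case report forms proved to lack the lever arm, which the available documents neither show nor suggest.
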